**Table 2: Potential Adverse Events Related to DSF**

MedDRA Term	Frequency: Likely: greater than 10% Less Likely: 1-10% Rare: 1% or less
Neoplasms	Rare: Tumor necrosis
Blood and lymphatic system disorders	Rare: Neutropenia, anemia, leukopenia, thrombocytopenia, lymphopenia (likely due to TMZ)
Immune system disorders	Rare: Hypersensitivity
Metabolism and nutrition disorders	Likely: Alcohol intolerance, metallic or garlic-like aftertaste
Psychiatric disorders	Less Likely: psychosis, delirium (need to rule out tumor progression)
Nervous system disorders	Likely: Drowsiness, headache, confusion Less Likely: ataxia, gait disturbance, peripheral neuropathy Rare: Extrapyrarnidal symptoms
Eye disorders	Rare: Optic neuritis
Cardiac disorders	Less Likely: Tachycardia, hypotension (need to rule out DSF-alcohol reaction)
Respiratory, thoracic, and mediastinal disorders	Less Likely: Dyspnea (need to rule out DSF-alcohol reaction)
Gastrointestinal disorders	Likely: Nausea, vomiting, diarrhea Less Likely: constipation (likely due to temozolomide)
Hepatobiliary disorders	Rare: Hepatitis
Skin and subcutaneous tissue disorders	Less Likely: Allergic dermatitis
Musculoskeletal	Rare: Arthralgia, myalgia
Renal and urinary disorders	Rare: Dysuria, hematuria

MedDRA Term	Frequency: Likely: greater than 10% Less Likely: 1-10% Rare: 1% or less
Reproductive system	Less likely: impotence
General disorders	Likely: Fatigue

#### 4.5 General Concomitant Medication and Supportive Care Guidelines

The following medications and procedures are prohibited during the study:

- Any antineoplastic therapy other than TMZ and DSF
- Any investigational therapy other than DSF

All other medical conditions or manifestations of the patient's malignancy should be treated at the discretion of the investigator in accordance with local community standards of medical care.

Patients should not drive, operate dangerous tools or machinery, or engage in any other potentially hazardous activity that requires full alertness and coordination if they experience sedation while enrolled in this study.

Patients are to be instructed to abstain from alcohol while enrolled in this study.

##### 4.5.1 Nausea and Vomiting

Prophylactic antiemetic therapy may be used in this study at the discretion of treating physician. Because of the potential of benzodiazepines to interact with DSF, the use of benzodiazepines for antiemetic prophylaxis should be reserved for patients who cannot be satisfactorily managed otherwise.

##### 4.5.2 Diarrhea

Antidiarrheal medications will not be used prophylactically; however, patients will be instructed to take loperamide, 4 mg, at the occurrence of the first loose stool and then 2 mg every 2 hours until they are diarrhea-free for at least 12 hours. During the night, patients may take 4 mg of loperamide every 4 hours. Fluid intake should be maintained to avoid dehydration.

##### 4.5.3 Central Nervous System Effects

Doses of 500-1000 mg of DSF per day with adjuvant TMZ produced neurological toxicities in some patients, including delirium/psychosis, ataxia, and peripheral neuropathy, especially at the 1000 mg dose. Patients should be carefully monitored for early signs of these symptoms. Once other causes such as tumor progression are ruled out, dose reduction of DSF to 40 mg (one capsule) three times daily should be considered if the toxicity is grade 2 or greater (refer to Section 6.2). If symptoms

are not improving with dose reduction, DSF should be discontinued. Patients whose symptoms are not considered immediately life-threatening should be carefully monitored. Each patient may be approached individually with a systematic assessment to rule out other causes. Appropriate tests may include vital signs measurement, computerized tomography, MRI scans, or other appropriate medical assessment.

If the patient's level of consciousness is considered to be life-threatening, the patient should be hospitalized and necessary measures should be instituted to secure the airway, ventilation, and intravenous access.

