### 3.2 Exclusion Criteria

1. Radiographic evidence of leptomeningeal dissemination, gliomatosis cerebri, infratentorial tumor, or metastatic disease to sites remote from the supratentorial brain.
2. Enrolled in another clinical trial testing a novel therapy or drug.
3. Received more than one course of radiation therapy or more than a total dose of 75 Gy. Subjects may have received radiosurgery as part of the initial therapy (i.e., in addition to one course of radiation therapy); however, the dose used for the radiosurgery counts against the total dose limit listed above.
4. History of allergic reaction to DSF or Cu.
5. Treatment with the following medications that may interfere with metabolism of DSF: warfarin, theophylline, amitriptyline, isoniazid, metronidazole, phenytoin, Phenobarbital, chlorzoxazone, halothane, imipramine, chlordiazepoxide, diazepam. (Note: lorazepam and oxazepam are not affected by the P450 system and are not contraindicated with DSF).
6. Active infection including known Acquired Immunodeficiency Syndrome (AIDS) or Hepatitis C or with a fever  $\geq$  38.5°C within 3 days prior to the study enrollment.
7. Active or severe hepatic disease.
8. Grade 2 or higher peripheral neuropathy or ataxia per NCI CTCAE version 4.
9. History of idiopathic seizure disorder schizophrenia, or psychosis unrelated to glioblastoma, corticosteroid, or anti-epileptic medications.
10. History of Wilson's disease.
11. History of hemochromatosis.

Commented [SM1]: Why?

12. Pregnant and breastfeeding women will be excluded because of the unknown effect of DSF on fetal development (and because of use of temozolomide).

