#### **6.2 Disulfiram Dose Modifications**

If a patient experiences any grade 2 or higher non-hematologic toxicity considered by the investigator to be possibly, probably, or definitely related to DSF, the dose of DSF may be decreased by 50% (i.e., from 80 mg TID to 40 mg TID) once. Special attention should be paid to neurological symptoms such as delirium/psychosis, gait disturbance/ataxia, and peripheral neuropathy. A grade 2 toxicity of the above neurological symptoms should prompt a consideration for further work-up and dose reduction. No second dose reduction is allowed—if a second dose reduction is required, DSF and Cu will be discontinued and the patient will be taken off study. Of note, hematologic toxicity is uncommon for DSF and is likely related to TMZ.

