##### **6.2.1 Administration of DSF to Patients with Abnormal Hepatic Function**

DSF-Cu should only be administered if hepatic function is within the parameters established in the eligibility criteria. Hepatic toxicity from DSF-Cu is uncommon but may occur. Therefore, hepatic dysfunction that occurs while the patient is on study should prompt an evaluation to determine the cause, including the possibility of hepatotoxicity from concurrent medications.

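### Neurotoxicity has one discretionary dose rule from grade 2 upward and no grade 3-4 hold or stop; separately, going off study under section 6.2 appears to end the 8-weekly MRI that PFS6 relies on

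*Combined protocol and SAP*

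**What the plan says.** **Dosing.** Section 4.5.3 sets the response to neurological toxicity: "dose reduction of DSF to 40 mg (one capsule) three times daily should be considered if the toxicity is grade 2 or greater". That step comes after a condition, "Once other causes such as tumor progression are ruled out". DSF stops under 4.5.3 only if symptoms "are not improving with dose reduction, DSF should be discontinued". When the level of consciousness is judged life-threatening, "the patient should be hospitalized and necessary measures should be instituted to secure the airway, ventilation, and intravenous access"; that paragraph says nothing about DSF or copper.

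Section 6.2 allows one 50% reduction (80 mg TID to 40 mg TID) for non-hematologic toxicity of grade 2 or higher that is at least possibly related to DSF. For the neurological symptoms it names one grade only: "A grade 2 toxicity of the above neurological symptoms should prompt a consideration for further work-up and dose reduction".

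Section 4.7 ends DSF for an adverse event that the investigator judges could cause severe or lasting harm. It also refers to adverse events delaying treatment. It names no grade.

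**Study status.** Section 6.2 continues: "if a second dose reduction is required, DSF and Cu will be discontinued and the patient will be taken off study". Section 4.7 lets TMZ go on after DSF-Cu is stopped for toxicity. Section 4.4 sets brain MRI every 8 weeks. Section 4.8 and footnote 1 of the study calendar (section 10.0) give routine or clinically indicated follow-up, with a chart review for progression and survival at two years. The calendar marks MRI at baseline, at the end of even-numbered cycles and at end of treatment. The Tumor Measurement Form (section 11.0) follows the same schedule.

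**The concern.** Neurotoxicity is the known serious risk of this drug in this disease. In phase I (sections 1.4 and 1.6), delirium and ataxia were dose-limiting at 1000 mg/day. At 500 mg/day, one patient had grade 3 delirium after 55 days and another had grade 3 motor neuropathy; both events resolved after DSF was stopped. Here the written response to such an event is the same as for grade 2: an optional halving. In a multi-center trial, an immediate hold or stop then depends on each investigator turning to 4.7, and sites may treat the same event differently.

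The study-status wording touches a co-primary endpoint. PFS6 under section 12.1 rests on RANO progression with 20 patients. If a patient leaves the study progression-free, the later progression date comes from scans at whatever interval routine care uses.

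**Working it through.** The plan gives no figure of its own on this point. The check is a comparison of texts, followed by sizing under stated assumptions.

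**1. Dosing rule by grade**

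| Situation | 4.5.3 | 6.2 | 4.7 |
|---|---|---|---|
| Grade 2 | consider 40 mg TID after ruling out other causes | may halve once; consider work-up | investigator judgment |
| Grade 3 | same as grade 2 | may halve once; grade not named for neurological symptoms | investigator judgment |
| Grade 4 or life-threatening | same tier; hospital and airway care, DSF not mentioned | may halve once | investigator judgment |
| No improvement, or second reduction needed | stop DSF | stop DSF and Cu, off study | investigator judgment |

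No cell holds or stops drug because of grade. Section 6.2.2, by contrast, requires an immediate stop without re-challenge for severe hypersensitivity, and 4.6 requires an immediate stop for suspected pregnancy, with restart allowed if it is excluded.

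**2. How often grade 3 or higher might occur**

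- Phase I at 500 mg/day (section 1.6, Table 1): 2/7 = 28.6%, exact (Clopper-Pearson) 95% CI 3.7% to 71.0%.
- Dose here: 3 × 80 = 240 mg/day; 240/500 = 0.48 of that dose. The 2/7 rate does not carry over directly.
- Table 2 of section 4.4 lists delirium, ataxia and peripheral neuropathy at 1-10%, without grade.
- Assumed grade 3+ rate r, with n = 20. Expected events = 20r; P(at least one) = 1 − (1 − r)^20.

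| r | Expected | P(at least one) |
|---|---|---|
| 2% | 0.4 | 0.332 |
| 5% | 1.0 | 0.642 |
| 10% | 2.0 | 0.878 |

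**3. Patients who lose scheduled MRI**

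Assume a fraction q of patients would reach a toxicity stop with off-study status at week t, independently of progression. The expected number still progression-free at that point is 20 × q × S(t), with exponential PFS:

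- Comparator (section 1.2, median 7.5 weeks): S0(t) = 0.5^(t/7.5). S0(26) = 0.090, which agrees with the comparator's reported PFS6 of 9%.
- Target (section 12.1, PFS6 30%): S1(t) = exp(ln 0.30 × t/26).

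| t (weeks) | S0(t) | S1(t) | q = 2% | q = 5% | q = 10% |
|---|---|---|---|---|---|
| 4 | 0.691 | 0.831 | 0.28-0.33 | 0.69-0.83 | 1.38-1.66 |
| 8 | 0.477 | 0.690 | 0.19-0.28 | 0.48-0.69 | 0.95-1.38 |
| 16 | 0.228 | 0.477 | 0.09-0.19 | 0.23-0.48 | 0.46-0.95 |

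The overall range is 0.1 to 1.7 of 20 patients.

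**4. What one patient is worth**

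1/20 = 5 percentage points. In an exact one-sided test against 10%, P(X ≥ 4) = 0.133 and P(X ≥ 5) = 0.043 for n = 20, so one patient's status can move the result across the plan's approximate 0.10 level.

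**The case against.** The strongest reply is that the protocol already provides ways to act. Section 4.7 ends DSF for an adverse event judged to risk severe harm, and a life-threatening level of consciousness fits that on any ordinary reading. Its mention of treatment delays presupposes that dosing can be interrupted. Section 6.2 permits reduction for merely possibly related toxicity, without first excluding other causes. All of this stands. A reader might infer that DSF cannot be stopped for a grade 3-4 event, or that full dose must continue during work-up. The documents support neither: 4.5.3 read alone leaves full dose possible during work-up, but nothing requires it.

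Two comparisons with other parts of the protocol are weaker than they look. Section 6.2.1 says "DSF-Cu should only be administered if hepatic function is within the parameters established in the eligibility criteria", but for hepatic dysfunction arising on study it asks only for an evaluation of the cause. The exclusion of "Grade 2 or higher peripheral neuropathy or ataxia per NCI CTCAE version 4" is an entry criterion, and entry criteria are not ordinarily continuation rules. It offers a convenient restart limit and does not show an error.

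The risk may also be low. The lung cancer study at 40 mg TID reported no significant neurological toxicity except fatigue, and the ongoing cohort on 500 mg DSF with copper is described as well tolerated so far (section 1.7). Divided dosing was chosen partly for tolerability.

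On imaging, no sentence says that MRI stops; that is inferred from four places. An end-of-treatment MRI is scheduled, routine scans may continue, and the chart review collects progression. A reader might infer that PFS6 is lost for these patients. What is lost is the fixed schedule, and because routine scan intervals are not stated, misclassification cannot be quantified. Follow-up of adverse events to resolution is unaffected.

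**Conclusion.** The point holds as a gap in firmness: neurotoxicity has no grade-based hold or stop at grade 3-4, and the life-threatening paragraph omits the study drugs. The remedy that preceded recovery in both phase I patients at 500 mg/day is left to general discretion. How many patients this touches is unknown; 0.4 to 2 of 20 rests entirely on the assumed 2-10% rates.

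The imaging point is a sound inference of small size: 0.1 to 1.7 of 20 patients, given exponential PFS, stops between weeks 4 and 16, and 2-10% of patients stopping this way. The 5 points per patient is a ceiling, reached only if that patient's six-month status is wrong.

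Severity is minor to moderate. The text and arithmetic are firm; the event rates are not.

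**What to change.** (a) **Section 6.2.** For grade 3 delirium/psychosis, ataxia/gait disturbance or peripheral neuropathy at least possibly related to DSF, hold DSF and Cu at onset and during work-up. Resume if another cause is established. Otherwise restart at 40 mg TID only once below grade 2, or discontinue. For grade 4, discontinue permanently. Leave grade 2 reduction discretionary.

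(b) **Section 4.5.3.** Add an instruction to stop DSF and Cu to the life-threatening paragraph, and state that ruling out other causes does not delay a grade 3-4 hold.

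(c) **Imaging.** In 6.2, have the patient come off DSF and Cu instead of off study. For anyone who stops DSF-Cu for toxicity without progression, whether under 4.5.3, 4.7 or 6.2, continue 8-weekly MRI to progression or month 6. Make matching edits to 4.8, the calendar (follow-up column and footnote 1) and the Tumor Measurement Form schedule; changing 6.2 alone would create a new inconsistency.

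**Cost.** One amendment touching about five sections (4.5.3, 6.2, 4.8, 10.0, 11.0). Over 26 weeks there are 26 × 7 × 3 = 546 DSF doses. A one-week hold loses 21 (3.8%) and a two-week hold 42 (7.7%), including in patients whose symptoms prove to have another cause. If that cause is progression, 4.7 stops TMZ and DSF-Cu anyway. Imaging adds at most three MRIs per affected patient (weeks 8, 16 and 24), on the existing schedule.

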#### **4.5.4 Management of Disulfiram-Alcohol Reaction**

In severe reactions caused by the patient's excessive ingestion of alcohol, supportive measures to restore blood pressure and treat shock should be instituted. Other recommendations include: oxygen, carbogen (95% oxygen and 5% carbon dioxide), vitamin C intravenously in massive doses (1 g), and ephedrine sulfate. Antihistamines have also been used intravenously. Potassium levels should be monitored, particularly in patients on digitalis, since hypokalemia has been reported.

#### **4.6 Women of Childbearing Potential**

Women of childbearing potential (defined as women with regular menses, women with amenorrhea, women with irregular cycles, women using a contraceptive method that precludes withdrawal bleeding, or women who have had a tubal ligation) are required to have a negative serum pregnancy test within 14 days prior to the first dose of the study treatment.

Female and male patients (along with their female partners) are required to use a method of acceptable contraception, including one barrier method, during participation in the study and for 4 months following the last dose of study treatment.

If a patient is suspected to be pregnant, study treatment should be immediately discontinued. In addition a positive urine test must be confirmed by a serum pregnancy test. If it is confirmed that the patient is not pregnant, the patient may resume treatment.

If a female patient or female partner of a male patient becomes pregnant during therapy or within 4 months after the last dose of study treatment, the investigator must be notified in order to facilitate outcome follow-up.

#### **4.7 Duration of Therapy**

If at any time the constraints of this protocol are considered to be detrimental to the patient's health and/or the patient no longer wishes to continue protocol therapy, the

protocol therapy should be discontinued and the reason(s) for discontinuation documented in the case report form.

In the absence of treatment delays due to adverse events, DSF treatment may continue until:

- Documented and confirmed disease progression
- Death
- Adverse event(s) that, in the judgment of the investigator, may cause severe or permanent harm or which rule out continuation of study drug
- General or specific changes in the patient's condition render the patient unacceptable for further treatment in the judgment of the investigator
- Suspected pregnancy
- Serious noncompliance with the study protocol
- Lost to follow-up
- Patient withdraws consent
- Investigator removes the patient from study
- The sponsor (Cantex), the investigator, or the investigator's institution decides to close the study

In the case of tumor progression, both TMZ and DSF-Cu should be discontinued, and patient should be considered for second-line therapy. If TMZ is temporarily withheld due to toxicity, DSF-Cu should be continued until TMZ may be resumed again. If TMZ is discontinued, DSF-Cu may be continued as per the discretion of the treating physician. If DSF-Cu is discontinued due to toxicity, TMZ may be continued as per the discretion of the treating physician.

#### **4.8 Duration of Follow-up**

Patients are evaluated for adverse events for 30 days after the last dose of DSF-Cu or until death, whichever occurs first. Patients removed from study for unacceptable adverse events will be followed until resolution or stabilization of the adverse event. Follow-up after the conclusion of the study participation will be per routine clinical care. Two years after the patient goes off study, the patient's chart will be reviewed to collect data on progression and survival.

### **5.0 RESPONSE ASSESSMENT**

For the purposes of this study, patients should be evaluated for response every 8 weeks

Response and progression will be evaluated in this study using the updated RANO response assessment criteria for high-grade gliomas (Wen, et al. 2010).

Criteria for Determining First Progression Depending on Time from Initial Chemoradiotherapy

First Progression	Definition
Progressive disease < 12 weeks after completion of chemoradiotherapy	Progression can only be defined using diagnostic imaging if there is new enhancement outside of the radiation field (beyond the high-dose region or 80% isodose line) or if there is unequivocal evidence of viable tumor on histopathologic sampling (eg, solid tumor areas [ie, > 70% tumor cell nuclei in areas], high or progressive increase in MIB-1 proliferation index compared with prior biopsy, or evidence for histologic progression or increased anaplasia in tumor). Note: Given the difficulty of differentiating true progression from pseudoprogression, clinical decline alone, in the absence of radiographic or histologic confirmation of progression, will not be sufficient for definition of progressive disease in the first 12 weeks after completion of concurrent chemoradiotherapy.
Progressive disease ≥ 12 weeks after chemoradiotherapy completion	
 
1. New contrast-enhancing lesion outside of radiation field on decreasing, stable, or increasing doses of corticosteroids.
 
2. Increase by ≥ 25% in the sum of the products of perpendicular diameters between the first post-radiotherapy scan, or a subsequent scan with smaller tumor size, and the scan at 12 weeks or later on stable or increasing doses of corticosteroids.
 
3. Clinical deterioration not attributable to concurrent medication or comorbid conditions is sufficient to declare progression on current treatment but not for entry onto a clinical trial for recurrence.
 
4. For patients receiving antiangiogenic therapy, significant increase in T2/FLAIR non-enhancing lesion may also be considered progressive disease. The increased T2/FLAIR must have occurred with the patient on stable or increasing doses of corticosteroids compared with baseline scan or best response after initiation of therapy and not be a result of comorbid events (eg, effects of radiation therapy, demyelination, ischemic injury, infection, seizures, postoperative changes, or other treatment effects).
 

Criteria for Response Assessment Incorporating MRI and Clinical Factors (Adapted from (Wen, et al. 2010).

Response	Criteria
Complete response	
 
• Requires all of the following: complete disappearance of all enhancing measurable and non-measurable disease sustained for at least 4 weeks.
 
• No new lesions; stable or improved non-enhancing (T2/FLAIR) lesions.
 
• Patients must be off corticosteroids (or on physiologic replacement doses only) and stable or improved clinically. Note: Patients with non-measurable disease only cannot have a complete response; the best response possible is stable disease.
 

Partial response	
Requires all of the following:
 
 
• ≥ 50% decrease compared with baseline in the sum of products of perpendicular diameters of all measurable enhancing lesions sustained for at least 4 weeks.
 
• No progression of non-measurable disease.
 

Response	Criteria
	
 
Stable or improved non-enhancing (T2/FLAIR) lesions on same or lower dose of corticosteroids compared with baseline scan; the corticosteroid dose at the time of the scan evaluation should be no greater than the dose at time of baseline scan.
 
Stable or improved clinically. Note: Patients with non-measurable disease only cannot have a partial response; the best response possible is stable disease.
 

Stable disease	Requires all of the following: 
 
Does not qualify for complete response, partial response, or progression.
 
Stable non-enhancing (T2/FLAIR) lesions on same or lower dose of corticosteroids compared with baseline scan. In the event that the corticosteroid dose was increased for new symptoms and signs without confirmation of disease progression on neuroimaging, and subsequent follow-up imaging shows that this increase in corticosteroids was required because of disease progression, the last scan considered to show stable disease will be the scan obtained when the corticosteroid dose was equivalent to the baseline dose.
 

Progression	Defined by any of the following: 
 
<math>\geq 25\%</math> increase in sum of the products of perpendicular diameters of enhancing lesions compared with the smallest tumor measurement obtained either at baseline (if no decrease) or best response, on stable or increasing doses of corticosteroids*. The absolute increase in any dimension must be at least 5mm when calculating the products.
 
Significant increase in T2/FLAIR non-enhancing lesion on stable or increasing doses of corticosteroids compared with baseline scan or best response after initiation of therapy* not caused by comorbid events (e.g. radiation therapy, demyelination, ischemic injury, infection, seizures, postoperative changes, or other treatment effects).
 
Any new measurable lesion.
 
Clear clinical deterioration not attributable to other causes apart from the tumor (e.g. seizures, medication adverse effects, complications of therapy, cerebrovascular events, infection, and so on) or changes in corticosteroid dose.
 
Failure to return for evaluation as a result of death or deteriorating condition; or clear progression of non-measurable disease.
 

- NOTE. All measurable and non-measurable lesions must be assessed using the same techniques as at baseline.
- Abbreviations: MRI, magnetic resonance imaging; FLAIR, fluid-attenuated inversion recovery.
- Stable doses of corticosteroids include patients not on corticosteroids.

